5.2 Inclusion criteria

Patients eligible for inclusion in this study have to meet **all** of the following criteria:

1. Prior to any screening procedures being performed, written informed consent/assent must be provided. For pediatric patients, consent will be obtained from the parent(s) or the patient's legal representative. Investigators will also obtain assent of patients according to local, regional or national guidelines.
2. Male and female patients aged ≥ 2 years
3. Deferasirox naïve patient or a chelation naïve patient or a patient treated by other chelators for at least 6 months continuously, such as:
 - a. Deferiprone (DFP)
 - b. Deferoxamine (DFO)
 - c. Combination (DFO + DFP)
4. Subject is willing to discontinue current iron chelation therapy at least 5 days prior to the Study day 1 and for the duration of the study
5. Patients with transfusion-dependent thalassemia (independent of underlying condition) with transfusional iron overload as shown by:
 - a serum ferritin level of > 1000 ng/ml at screening and if available, LIC > 3 mg Fe/g dw within 6 months prior to screening
6. Patients with non-transfusion-dependent thalassemia with iron overload as shown by:
 - a serum ferritin level of ≥ 800 ng/ml at screening and if available, LIC ≥ 5 mg Fe/g dw within 6 months prior to screening

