6.2.1.3 Changes in Serum Ferritin

Serum ferritin should be monitored monthly during the study as stated in the Visit Evaluation Schedule [Table 7-1](#) and [Table 7-2](#).

For ICT pre-treated patients, the dose of deferasirox DT should be adjusted if necessary every 3 months based on the trends in serum ferritin and investigator's judgement. [Table 6.2](#) provides additional guidance on suggested doses.

Dose adjustments should be made in steps of 5-10 mg/kg/day for deferasirox DT and of 3.5-7 mg/kg/day for deferasirox FCT and are to be tailored to the individual patient's response and therapeutic goals (maintenance or reduction of iron burden).

For TDT patients not adequately controlled with:

- Deferasirox DT doses of 30 mg/kg/day, doses of up to 40 mg/kg/day may be considered. Doses above 40 mg/kg/day are not permitted.
- Deferasirox FCT doses of 21 mg/kg/day, doses of up to 28 mg/kg/day may be considered. Doses above 28 mg/kg/day are not permitted.

For NTDT patients not adequately controlled with:

- Deferasirox DT doses of 15 mg/kg/day, doses of up to 20 mg/kg/day may be considered. Doses above 20 mg/kg/day are not permitted.
- Deferasirox FCT doses of 10.5 mg/kg/day, doses of up to 14 mg/kg/day may be considered. Doses above 14 mg/kg/day are not permitted.

In patients whose serum ferritin level has reached the target (usually between 500 and 1000 ng/mL for TDT patients or between 300-800 ng/mL for NTDT patients), dose reductions in steps of 5-10 mg/kg/day for deferasirox DT and of 3.5-7 mg/kg/day for deferasirox FCT should be considered to maintain serum ferritin levels within the target range.

If serum ferritin falls below 500 ng/mL for TDT patients and 300 ng/mL for NTDT patients, an interruption of study treatment should be considered until serum ferritin rises above 500 ng/mL or 300 ng/mL respectively.

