### **2.5.4 Supportive analyses**

Sensitivity analyses and supportive analyses will be conducted in order to provide evidence that the results seen from the primary analysis are robust.

In order to support the Mc Nemar's test for matched pair, the Odd's Ratio (OR) of patient preference (i.e.  $OR=p_{12}/p_{21}$ ), 95% CI and p-values will also be presented. Conditional logistic model for matched pair analyses may also be fitted if feasible.

The primary and above supportive analyses will also be performed for each subgroup of the baseline factor, i.e. on patients with TDT or NTDT and also on prior treatment status of iron chelation (naïve or pre-treated). Additionally, the primary analysis will be performed by age groups: 2-6 years (infant), 7-11 years (child), 12-17 years (adolescent), < 18 years (overall of infant, child and adolescent), and  $\geq 18$  years (adult). No p-values will be presented for subgroup analyses.

To identify the impact of preference on switching, the primary analyses will be performed separately for patients with or without switching before Week 48.

As a supportive analysis, the primary analysis will also be provided for PPS.

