| I03b                | Subjects being treated with other chelators during the 6 months within study participation.   | EXCLUDE FROM PPS             | 4                    |
| I03c                | Subjects being treated with DFP or DFO or combination (DFP+DFO) at least 6 months continuously.   | EXCLUDE FROM PPS             | 4                    |
| I04                 | Subject is not willing to discontinue current iron chelation therapy at least 5 days prior to the first day and for the duration of the study   | EXCLUDE FROM PPS             | 4                    |
| I05                 | Patients with transfusion-dependent thalassemia (independent of underlying condition) with transfusional iron overload as shown by: a serum ferritin level of <=1000 ng/ml at screening and if available, LIC <= 3 mg Fe/g dw until 6 months prior to screening | INCLUDE IN EVERYTHING        | 0                    |

| Deviation ID | Description of Deviation   | Exclusion in Analyses | Severity code |
|---------------------|---|------------------------------|----------------------|
| I06                 | Patients with non-transfusion-dependent thalassemia with iron overload as shown by: a serum ferritin level of < 800 ng/ml at screening and if available, LIC < 5 mg Fe/g dw until 6 months prior to screening | INCLUDE IN EVERYTHING        | 0                    |
| I07a                | Date informed consent obtained from subject after screening procedures  | INCLUDE IN EVERYTHING        | 0                    |
| I07b                | Date informed consent obtained from parent(s) or legal patient's representative obtained after screening procedures   | INCLUDE IN EVERYTHING        | 0                    |
| M01                 | Use of Prohibited medication as per protocol section 6.3.2.   | EXCLUDE FROM PPS             | 4                    |
| M02                 | Any investigational drug other than the study drug  | EXCLUDE FROM PPS             | 4                    |
| S01                 | Starting dose of deferasirox DT is not compliant with Protocol table 6-2.   | EXCLUDE FROM PPS             | 4                    |
| S02                 | Starting dose of deferasirox FCT is not compliant with Protocol table 7-3.  | EXCLUDE FROM PPS             | 4                    |

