| S03                 | Deferasirox DT and/or FCT is not compliant with Protocol table 6-3 based on serum ferritin levels.  | EXCLUDE FROM PPS             | 4                    |
| S04                 | Study dose should be adjusted if there is a change in body weight (increase or decrease) of minimum 10% compare to visit 2 or last dose adjustment due to change in patient's body weight.                    | EXCLUDE FROM PPS             | 4                    |
| S05                 | Patient in period 1 of Core phase received Deferasirox FCT by error (except patients who switched from Deferasirox DT to Deferasirox FCT)   | EXCLUDE FROM FAS             | 1                    |
| S06                 | Patient in period 2 of Core phase or extension phase took Deferasirox DT by error (except patients who switched from Deferasirox FCT to Deferasirox DT).  | EXCLUDE FROM FAS             | 1                    |
| S07a                | Patient re-switched treatment within the same period of the study (that is, patient switched from Deferasirox DT to Deferasirox FCT and the switch back to Deferasirox DT)                                    | EXCLUDE FROM FAS             | 1                    |
| S07b                | Patient re-switched treatment within the same period of the study (that is, patient switched from Deferasirox FCT to Deferasirox DT, and then back to Deferasirox FCT)  | EXCLUDE FROM FAS             | 1                    |

| Deviation ID | Description of Deviation   | Exclusion in Analyses | Severity code |
|--------------|--|-----------------------|---------------|
| S08          | Iron chelation pre-treated patient who is well-managed on treatment with deferoxamine DFO/deferiprone DFP or combination of DFO+DFP did not receive the equivalent deferasirox DT/FCT dose per app. 14.1 | EXCLUDE FROM PPS      | 4             |
| S09          | Dose adjustment (based on Serum ferritin levels and investigator's judgement) in ICT naïve patients done before 4 weeks of study treatment and it was not performed for safety reasons                   | EXCLUDE FROM PPS      | 4             |
| S10          | Dose adjustment (based on Serum ferritin levels and investigator's judgement ) ICT pre-treated patients done before 3 months of study treatment and it was not performed for safety reasons              | EXCLUDE FROM PPS      | 4             |

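### SAP 5.5 row I03c codes the protocol's prior-chelator eligibility criterion as a reason for exclusion from the Per-Protocol Set, and row S03 cannot always be met together with other exclusion rows

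*SAP*

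**What the plan says.** Protocol 5.2, criterion 3, admits a "Deferasirox naïve patient or a chelation naïve patient or a patient treated by other chelators for at least 6 months continuously, such as" DFP, DFO or the two combined. The population statement in the protocol summary adds that a pre-treated patient must have had other chelators continuously for at least 6 months.

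SAP 2.2 defines the PPS as the FAS patients who comply with the protocol and have no major deviation, and refers to SAP 5.5 for the list. Table 1 there gives code 4 (exclude from PPS) to these rows among others:

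- I03c: "Subjects being treated with DFP or DFO or combination (DFP+DFO) at least 6 months continuously".
- I03b: "Subjects being treated with other chelators during the 6 months within study participation".
- S01: "Starting dose of deferasirox DT is not compliant with Protocol table 6-2".
- S03: "Deferasirox DT and/or FCT is not compliant with Protocol table 6-3 based on serum ferritin levels".
- S09 and S10: ferritin-based adjustment before 4 weeks (naïve) or 3 months (pre-treated).
- S15 and S16: maximum DT or FCT dose not in line with Table 6-2.
- S17 and S18: DT or FCT adjustment not in line with Table 6-2.

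Rows S11 and S12, on the size of adjustment steps, carry code 0 (include in everything). On the use of the set, SAP 2.5.4 says: "As a supportive analysis, the primary analysis will also be provided for PPS".

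**The concern.** A per-protocol analysis should keep patients who followed the protocol and drop those who did not. Row I03c does the reverse for one eligible group, since a programmer who follows the table flags patients for having met criterion 3. Row S03 has a different fault. Read with its neighbours, it can leave a patient with no dose that avoids a code-4 flag. In both cases the PPS would be selected by prior therapy or ferritin rather than by adherence, and comparing it with the FAS would no longer test whether the preference result depends on protocol compliance.

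**Working it through.** **1. The plan's sample size.** SAP section 3 and Protocol 10.8 give p12 = 0.45 (FCT preferred), p21 = 0.25 (DT preferred), two-sided alpha 0.05, 80% power and McNemar's test. The discordant proportion is pd = 0.70 and the difference is d = 0.20. With the Wald variance:

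n = (1.960 + 0.842)² × (pd − d²) / d² = 7.849 × 0.66 / 0.04 = 129.5, so 130.

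Then 130 / 0.90 = 144.4, so 145. Both planned figures reproduce. The variant with the null variance gives 135, so the Wald form is the one that matches the plan.

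**2. I03c against criterion 3.** The rows around it describe a failure: I02 is age under 2 years, I04 is unwillingness to stop current chelation, and I05 and I06 are ferritin at or below the entry limit. I03c describes the criterion as satisfied and contains no negative. Under SAP 5.5 Table 2, code 4 removes a patient from the PPS but not from the FAS or the Safety Set.

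**3. Size of the I03c loss.** The documents do not give the pre-treated share, so it is an assumption, shown as a range. It is applied to the 130 evaluable patients and takes all pre-treated patients to have had DFP, DFO or both. Power = Φ(d√n / √(pd − d²) − 1.960).

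| Share removed | n left | Power, Wald | Power, exact McNemar |
|---|---|---|---|
| 0% | 130 | 80% | 76% |
| 25% | 98 | 68% | 63% |
| 50% | 65 | 51% | 44% |
| 75% | 32 | 29% | 20% |

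Example at n = 65: 0.20 × 8.062 / 0.8124 − 1.960 = 0.025, and Φ(0.025) = 0.51. These figures assume that the preference split is the same in the patients who remain. Exclusions under other rows would come on top.

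**4. S03 against the other code-4 rows (DT, mg/kg/day).**

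| Patient | Table 6-2 | Table 6-3 | Rows in conflict |
|---|---|---|---|
| Naïve TDT, ferritin >1500–2000 ng/mL | start 20 | 30 | S01 or S09 against S03, if S03 applies from Day 1 |
| Naïve TDT, >2000 | start 20 | 40 | same |
| Naïve NTDT, >2000–4000 | start 10 | 20 | same |
| NTDT, >4000 | maximum 20 | 30 | S15 against S03, at any time |

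In the first three rows, starting on Table 6-2 departs from Table 6-3, starting on Table 6-3 breaks S01, and moving before week 4 for ferritin breaks S09. In the last row no dose satisfies both tables. The FCT figures repeat the conflict (maximum 14 against 21), with S16 in place of S15. Protocol 6.2.1.3 repeats the NTDT maximum.

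**5. Adjustment steps.** The Table 6-2 adjustment column is 5–10 (DT) or 3.5–7 (FCT). Missing those increments is code 0 under S11/S12, while an adjustment that departs from Table 6-2 is code 4 under S17/S18. The same departure can therefore be kept or excluded.

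**The case against.** I03c looks like a dropped negative. The table is headed as a list of deviations, the definition in SAP 2.2 protects compliant patients, and S04 is also phrased as a requirement whose breach is meant. A careful programmer might apply the intended meaning. That is fair as to likely impact, and the documents do not show how the flags were derived. It does not rescue the wording: S04 states an obligation that can be breached, whereas I03c only describes a patient's history.

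Several objections limit the S03 part, and they stand:

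- Table 6-2 separates the start (weeks 1–4) from later adjustment, and the pointer to ferritin-based dosing in Protocol 6.1.1 closes a paragraph on adjustments. S03 can therefore be read as governing later dosing only. The first three conflicts in the table then fall away at the start of treatment; the NTDT conflict above 4000 ng/mL does not.
- S08 covers only pre-treated patients described as well managed on their earlier chelator, so it does not bind every DFO-pre-treated patient.
- A TDT ferritin below 1000 ng/mL has no row in Table 6-3. With no listed dose to depart from, a breach of S03 is not established.
- Section 6.2.1.3 treats the ferritin doses as guidance, but its pointer names Table 6.2. Applying that sentence to Table 6-3 assumes a cross-reference slip.

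A reader might also infer that I03b repeats the I03c error. Its wording fits on-study chelator use equally well, so it is ambiguous, not shown to be wrong.

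**Conclusion.** The point holds, as a should-fix matter confined to the supportive PPS analysis. I03c is wrong as written: taken literally it removes every eligible patient pre-treated with DFP, DFO or both, and the PPS result could not be interpreted as a per-protocol check. S03 is under-specified, and for NTDT patients with ferritin above 4000 ng/mL it cannot be met together with S15/S16.

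Three stronger readings are not supported:

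- That the primary result is compromised. SAP 2.5.1 bases it on the FAS, which code 4 does not touch.
- That all pre-treated patients are lost. I03c names only DFP, DFO and their combination, while criterion 3 gives these as examples and SAP 2.3.3 has a category for other chelators.
- That a known number of patients is lost, or that only a small low-ferritin group remains. Neither the pre-treated share nor the ferritin distribution is given, so the power figures illustrate a range of assumed shares.

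**What to change.** - Reword I03c as the violation: a pre-treated patient who was not treated continuously with other chelators for at least 6 months. Base it on the population statement in the protocol summary, because criterion 3 read alone could also admit a deferasirox-naïve patient with shorter prior chelation.
- State whether I03b means chelator use before or during the study.
- State the time point at which S03 applies. Reconcile S03 with S01, S08–S10, S11/S12 and S15–S18, and with Protocol Tables 6-2 and 6-3 and Section 6.2.1.3, so that a patient dosed as the protocol allows is not coded 4. No view is taken here on which dose is right.
- Confirm and document how I03c and S03 were applied in any PPS flags already derived, then re-derive the flags under the corrected rows.

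The cost is a revision of a few rows in SAP 5.5, reconciliation of the protocol passages named, and a re-run of the PPS derivation and its analysis. No new data are needed.

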10.1 Analysis sets

The following analysis sets will be used in this trial.

Enrolled Set

The Enrolled Set comprises of all patients enrolled in this study.

Full Analysis Set

The Full Analysis Set (FAS) comprises all patients to whom study treatment has been assigned and who received at least one dose of each study treatment (DT and FCT). Patients will be analyzed according to the treatment they have been assigned to.

Safety set

The Safety Set includes all patients who received at least one dose of either study treatment (DT or FCT), and at least one safety assessment on or after Day 1.

Patients will be analyzed according to the study treatment received, where treatment received is defined as the assigned treatment if the patient took at least one dose of that treatment or the first treatment received if the assigned treatment was never received.

Per-Protocol set

The Per-Protocol Set (PPS) consists of a subset of the patients in the FAS who are compliant with requirements of the CSP (clinical study protocol) without any major protocol deviation.

The major protocol deviations that will lead to exclusion of patients from the PPS will be detailed in the SAP.

Pharmacokinetic analysis set

Not applicable

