## 1 Introduction

This analysis plan module describes the statistical methods which will be used in the Phase II clinical study CICL670FIC05.

The main purpose of this document is to provide a summary of the statistical methodology that will be used for this clinical study; this includes a detailed description of data summaries. Analyses plan in this document refers to the related statistical analysis sections in the clinical study report.

The analysis described here will be conducted by Novartis using statistical software SAS® Version 9.4 according to the Statistical methods and data analysis Section 10 of the study protocol which will be available in Appendix 16.1.1 of the CSR. Important information will be given in the following sections and further details are provided, as applicable, in the Appendix 16.1.9 of the CSR.

Unless otherwise specified, the statistical methodologies including the analysis sets, analysis models, algorithms and conventions are following the Oncology study protocol CICL670FIC05 final version.

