## 2.2 Analysis sets

The following analysis sets will be used in this study.

**Enrolled Set:** The Enrolled Set comprises all patients enrolled in this study. Patients who discontinued from the study due to ineligibility immediately after Visit 2 are not considered as enrolled.

**Full Analysis Set (FAS):** The Full Analysis Set comprises all patients to whom study treatment has been assigned and who received at least one dose of each study treatment (DT and FCT). Patients will be analyzed according to the treatment they have been assigned to.

**Safety Set (SAF):** The Safety Set includes all patients who received at least one dose of either study treatment (DT or FCT), and at least one safety assessment on or after Day 1.

Patients will be analyzed according to the study treatment received, where treatment received is defined as the assigned treatment if the patient took at least one dose of that treatment or the first treatment received if the assigned treatment was never received.

**Per-Protocol Set (PPS):** The Per-Protocol Set consists of a subset of the patients in FAS who are compliant with requirements of the clinical study protocol (CSP) without any major protocol deviation.

Any major protocol deviation will lead to exclusion of patients from PPS. The list of PDs is defined in [Section 5.5](#).

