### **2.5.1 Primary endpoint**

The primary endpoint is the proportion (and percentage, %) of patients who claim preference of deferasirox FCT over deferasirox DT as measured by preference questionnaire at Week 48.

The analysis of primary variable will be based on the FAS.

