**Table 2 Analysis set exclusions based on population codes**

| Analysis set | Population codes that cause a subject to be excluded |
|--------------|--|
| RAN          | NA   |
| SAF          | 2, 3, 6  |
| FAS          | 1, 3   |
| PPS          | 4, 6   |

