**Table 3 Population code text**

| Population Code | Population code text                 |
|-----------------|--------------------------------------|
| 0               | INCLUDE IN EVERYTHING                |
| 1               | EXCLUDE FROM FULL ANALYSIS SET (FAS) |
| 2               | EXCLUDE FROM SAFETY SET (SAF)        |
| 3               | EXCLUDE FROM FAS AND SAF             |
| 4               | EXCLUDE FROM PER-PROTOCOL SET (PPS)  |
| 6               | EXCLUDE FROM SAF AND PPS             |

Unless otherwise stated, summary tables, figures and listings will be on all subjects included in the analysis set under consideration.

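### SAP 5.5 removes from the primary-analysis FAS patients (E10, S05, S06, S07a, S07b) whom protocol 10.1 and SAP 2.2 keep in it; S06 has no Week 48 cut-off, and SAP 4 records no change.

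*SAP*

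**What the plan says.** SAP 2.2, in the same words as protocol 10.1, states that the FAS "comprises all patients to whom study treatment has been assigned and who received at least one dose of each study treatment (DT and FCT"). Neither definition carries a deviation-based exclusion. Deviations enter only through the PPS. Protocol 10.1 says that "The major protocol deviations that will lead to exclusion of patients from the PPS will be detailed in the SAP", and SAP 2.2 points to Section 5.5 directly after its PPS rule. SAP 1 adds that, unless otherwise specified, the methods "including the analysis sets, analysis models, algorithms and conventions are following the Oncology study protocol". For the primary endpoint, SAP 2.5.1 says: "The analysis of primary variable will be based on the FAS".

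SAP 5.5 works differently. Table 1 gives code 1 to five deviations:
- E10: taking part in another trial or receiving an investigational drug.
- S05: FCT received by error in period 1.
- S06: DT taken by error in period 2 or in the extension phase.
- S07a and S07b: re-switching within a period. S07a reads "patient switched from Deferasirox DT to Deferasirox FCT and the switch back to Deferasirox DT"; S07b is the mirror image.

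Table 3 gives the meaning of code 1 as "EXCLUDE FROM FULL ANALYSIS SET (FAS"). Table 2, under "Population codes that cause a subject to be excluded", lists codes 1 and 3 for the FAS, codes 2, 3 and 6 for the Safety Set, and codes 4 and 6 for the PPS. SAP 4, which should list changes to protocol-specified analyses, is marked as not applicable.

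**The concern.** The SAP holds two rules for who enters the primary test, and they give different answers for some patients. Four of the five codes (S05, S06, S07a, S07b) describe events after treatment has begun, so one rule conditions the primary population on what happened during the trial. For re-switchers it is plausible that going back to the earlier formulation relates to which one they like. That is my inference; the SAP does not say it. If it is right, removing them could bias the preference comparison in either direction.

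The missing cut-off in S06 adds a timing problem. The primary analysis is run once all patients have completed Week 48, and SAP 2.1 also foresees analysis at study end. An intake error in the extension could then take out a patient whose Week 48 answer had already been counted.

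**Working it through.** **Membership, code by code.** The test is whether a patient with the code can satisfy the FAS definition (treatment assigned, at least one dose of DT and one of FCT).
- S07a and S07b: a switch and a switch back require doses of both. The definition is always met, so the conflict is certain.
- E10, S05, S06: the definition is met whenever both formulations were taken. Otherwise the patient is outside the FAS under either rule.
- E17 (code 3; psychiatric or addictive disorder, or unable or unwilling to comply): the same conflict arises for dosed, consented patients. Code 3 also removes them from the Safety Set, which SAP 2.2 defines by one dose of either formulation and one safety assessment.
- D02 (code 3; never treated) agrees with the definition. I01a and I01b (code 3) concern absent consent and are not in dispute here.

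**Internal check of 5.5.** The PPS is defined as a subset of the FAS, yet the PPS row of Table 2 lists only codes 4 and 6. A code-1 patient is therefore coded out of the FAS but not out of the PPS. Also, E10 leaves the FAS for receiving an investigational drug, while the overlapping M02 leaves only the PPS.

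**The plan's own sample size.** With p12 = 0.45, p21 = 0.25, two-sided alpha 0.05 and 80% power (SAP 3):
n = (1.960 + 0.842)² × (0.70 − 0.20²) / 0.20² = 7.849 × 0.66 / 0.04 = 129.5, so 130; 130 / 0.90 = 144.4, so 145. Both figures reproduce. By the same formula, power is 80.2% at 130, 78.6% at 125 and 76.9% at 120. Losing a few patients at random costs little; selective loss is what matters.

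**Illustration of selective loss (assumed counts).** Take 130 patients left after the 5.5 exclusions, with preferences at the planned rates: 58.5 for FCT and 32.5 for DT. Then return k removed patients who all prefer DT. With b for FCT and c for DT, exact p = 2 × P(X ≥ b) for X binomial(b + c, 1/2); asymptotic chi-square = (b − c)² / (b + c) on 1 df. As 58.5 and 32.5 are not whole numbers, all four roundings are shown.

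| Start, FCT vs DT | Exact p | Asymptotic p | Smallest k for exact p > 0.05 | Smallest k for asymptotic p > 0.05 |
|---|---|---|---|---|
| 58 vs 33 | 0.0115 | 0.0088 | 5 (58 vs 38: 0.0519) | 6 (58 vs 39: 0.0537) |
| 58 vs 32 | 0.0080 | 0.0061 | 6 (58 vs 38: 0.0519) | 7 (58 vs 39: 0.0537) |
| 59 vs 33 | 0.0088 | 0.0067 | 6 (59 vs 39: 0.0544) | 7 (59 vs 40: 0.0562) |
| 59 vs 32 | 0.0061 | 0.0046 | 7 (59 vs 39: 0.0544) | 8 (59 vs 40: 0.0562) |

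So the range is 5 to 7 for the exact test and 6 to 8 for the asymptotic one. At 58 vs 38 the chi-square is 20² / 96 = 4.17, p = 0.041, so the two reported p-values fall on opposite sides of 0.05. Returning five patients from 58 vs 33 moves the FCT share from 58/130 = 44.6% to between 58/135 = 43.0% and 63/135 = 46.7%.

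The reverse case starts with the planned split in the defined FAS and lets 5.5 remove only FCT-preferrers. Removing 8 gives z = (50.5 − 32.5) / √83 = 1.98; removing 10 gives z = (48.5 − 32.5) / √81 = 1.78, no longer significant.

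**The case against.** The best defence is that SAP 1 follows the protocol only where nothing else is specified, and that 5.5 does specify something else in an operational table. On that view 5.5 is the detailed rule that 2.2 failed to summarise, and a reader can work out the population from it. This has some force, so it would go too far to say that the primary population cannot be determined. But SAP 2.2 restates the unqualified FAS and cites 5.5 only for the PPS, so the SAP contradicts itself. A deliberate departure should also appear in SAP 4.

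Re-switching is a genuine deviation, since protocol 4.2 forbids it within a period. That stands, but both definitions send deviations to the PPS.

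A reader might infer that the SAP itself ties these exclusions to preference, because 2.5.4 says: "To identify the impact of preference on switching, the primary analyses will be performed separately for patients with or without switching before Week 48". The text does not support that. It concerns switching, not re-switching; protocol 4.2 leaves switching to the investigator and names adverse events as a ground; S05 and S06 are errors that expressly except switchers; E10 is unrelated to switching.

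A reader might also infer that 5.5 was altered once results were known, or that the primary result will change at study end. The document history places an appendix update on 10-Jun-2020, before the interim lock, and nothing shows a later change to 5.5. The primary test is placed at Week 48. A different result later is possible only if FAS tables are rerun.

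**Conclusion.** The inconsistency is real and should be fixed. It rests on the texts alone: two rules for the primary set, certain to conflict for S07a and S07b, conditionally for E10, S05 and S06, and likewise for E17 in both the FAS and the Safety Set. S06 lacks a Week 48 limit, and Table 2 does not keep the PPS inside the FAS.

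Its effect on the result is unknown. The documents give no count of such patients, and with re-switching forbidden there may be few. At the planned effect, the conclusion would change only if several patients were removed and their preferences ran strongly one way. It would be tempting to say that five DT-preferring patients suffice, but that holds for one rounding and one of the two planned p-values. The illustration assumes that every returned patient states a preference and that the planned rates hold.

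Two neighbouring matters touch only the PPS and do not add to this point. I03c as worded excludes patients who meet inclusion criterion 3, probably through a dropped negative. For NTDT patients with ferritin above 4000 ng/mL, protocol Table 6-3 (30 mg/kg DT, 21 mg/kg FCT) exceeds the maxima in Table 6-2 and 6.2.1.3 (20 and 14), on which S03, S15 and S16 draw.

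**What to change.** - Recode E10, S05, S06, S07a and S07b from 1 to 4, so that SAP 5.5 agrees with the FAS of protocol 10.1 and SAP 2.2. As these patients would then leave the PPS by code, this also cures the Table 2 gap for them.
- For Week 48 analyses, count S06 only up to Week 48.
- Because this comes after the interim lock in an open-label study, enter it as a dated change in SAP 4 and in the CSR. Report the primary result under both the protocol 10.1 FAS and the 5.5 coding, with the number removed per code and their Week 48 answers, so that nothing depends on which set is preferred.
- Separately, keep the no-consent limb of E17 as it is and give the other limbs code 4, so that treated, consented patients stay in the FAS and the Safety Set.
- The sponsor must reconcile the I03c wording with criterion 3, and the NTDT dosing passages with each other, before S03, S15 and S16 are applied. No view is taken on which dose or table governs.

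Cost: no new data. The recoding needs a SAP addendum, a rerun of the Week 48 FAS tables and one extra table. E17 and I03c are edits to wording and codes; the E17 recode also means rerunning safety tables if any patient carries that code. The dosing reconciliation is a separate protocol clarification.
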